4.20.2 Benefits

Study subjects will receive systematic MINI assessment of their DSM comorbidity and subthreshold symptoms. This information will be readily available to their treating clinicians of PCP if the subjects so desire and agree to disclosure. This information might guide long term treatment if subjects are indeed symptomatic. In the short-term, the subject will receive close and systematic monitoring for anxiety and depressive symptoms and formalized cognitive assessments, beyond current standards of care. Easy access to routine physical exams are also a potential benefit.

5 Data Analysis Methods

5.1 General Considerations

The purpose of this study is to assess the change in cerebral blood flow induced by the Transcranial Continuous and Pulse Near-Infrared Light Therapy in healthy subjects

This study is expected to enroll 30 subjects and treat 10 subjects with TLT for a total study duration of 5 weeks.

5.2 Specific Primary Aim

To assess the change in cerebral blood flow induced by the Transcranial Continuous and Pulse Near-Infrared Light Therapy in healthy subjects

Hypothesis 1: We anticipate that p-TLT will trigger a significantly greater increase in CBF as compared to c-TLT, and c-TLT will trigger a significantly greater effect than sham (s-TLT). We expect that we will be also able to estimate the effect size of each type of TLT in terms of increase of CBF.

5.3 Sample Size

With respect to the TLT study, we expect 30 subjects to sign informed consent, including screen failures.

5.4 Subject Demographic and Baseline Characteristics

Subject demographic and baseline characteristics will be summarized. Descriptive summaries will include the number of subjects, mean, standard deviation, median, minimum and maximum for continuous parameters, frequencies and percentages for categorical parameters.

5.5 Efficacy Analyses for Primary Aims

For the primary analysis, delta CBF (measured with DCS-spectroscopy pre- and post-TLT) will be compared in all ten subjects by paired t-test. The primary comparisons will include: a) delta CBF for p-TLT and delta CBF for c-TLT subjects (n=20 within subject comparison) and b) delta CBF for c-TLT and delta CBF for s-TLT (n=20 within subject comparison).

5.6 Safety Analyses

The number and percent of Adverse Events through study completion will be presented by adverse event type.

5.7 *Additional Safety Analyses*

Descriptive statistics for safety endpoints will include number of subjects, mean, standard deviation, median minimum and maximum for continuous variables, and frequencies and percentages for categorical variables.

6 Ethical Review & Regulatory Considerations

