Study Population: Subjects eligible for study participation will be healthy by Structured Clinical Interview for Diagnostic Statistical Manual-IV (SCID) criteria. Subjects will be between 18-70 years of age (have not had 71st birthday) on the date of screening. Subjects who will be permitted into the study include those who meet all the inclusion criteria and have none of the exclusion criteria.

Duration of Participation:	Subjects will be followed in the study for 5 weeks.
Endpoints:	
Engagement of cerebral blood flow – The effect of TLT on cognition will be assessed before and after each session (c-TLT, s-TLT and p-TLT) by measuring the Diffuse Correlation Spectroscopy (DCS) signal.
 
Engagement of cerebral electrical activity – The effect of TLT on brain electrical waves will be assessed before and after each session (c-TLT, s-TLT and p-TLT) by measuring the Electro-Encephalographic (EEG) signal.
 
Engagement of cognitive circuitry – The effect of TLT on working memory will be assessed immediately after each session by n-back task.
 
Safety - The safety endpoints will evaluate any reported adverse events within one week from each sessions of TLT.

Entry Criteria: Inclusion Criteria	
	
 1. Subject's age at screening will be between 18 and 70 years old (inclusive). 2. Women of child-bearing potential must use a double-barrier method for birth control (e.g. condoms plus spermicide) if sexually active. 3. Subject Informed Consent obtained in writing in compliance with local regulations prior to enrollment into this study. 4. The subject is willing to participate in this study for at least 5 weeks.
Exclusion Criteria:	
	
 1. The subject is pregnant or lactating. 2. The subject is on any psychotropic medication. 3. Psychotherapy is exclusionary unless the subject has had at least 8 weeks of treatment prior to the screening visit. 4. Any current psychiatric disorder (per SCID assessment) 5. Substance or alcohol dependence or abuse in the past 6 months. 6. History of a psychotic disorder or psychotic episode (current psychotic episode per SCID assessment). 7. Bipolar affective disorder (per SCID assessment). 8. Unstable medical or neurological illness, defined as any illness which is not well-controlled with standard-of-care medications (e.g., insulin for diabetes mellitus, HCTZ for hypertension). 9. Suicidal or homicidal ideation as determined by SCID screening.

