4.1 Rationale

The specific aims of this study are:

1. To assess the change in cerebral blood flow induced by the Transcranial Continuous and Pulse Near-Infrared Light Therapy (c-TLT and p-TLT) in healthy subjects
2. To correlate with cognitive performance the change in cerebral blood flow induced by the Transcranial Continuous and Pulse Near-Infrared Light Therapy in healthy subjects
3. To correlate with brain electrical activity the change in cerebral blood flow induced by the Transcranial Continuous and Pulse Near-Infrared Light Therapy in healthy subjects
4. To correlate with skin pigmentation the change in cerebral blood flow induced by the Transcranial Continuous and Pulse Near-Infrared Light Therapy in healthy subjects
5. To assess the safety and tolerability of the Transcranial Continuous and Pulse Near-Infrared Light Therapy in healthy subjects

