4.3.1 Population Description

The subject population for this study will consist of healthy subjects between the ages of 18 and 70, of any ethnic background. We expect to enroll 30 subjects in order to have 10 who are eligible and complete the study. The subject will meet all the inclusion criteria, have none of the exclusion criteria, and provide their written Informed Consent to participate in this clinical study. In the event that a subject's ability to comprehend and communicate is compromised (per the assessment of the Investigator), local regulations pertaining to Informed Consent signatures should be followed.

Subjects will be recruited, via screenings, advertisements, and postings. Study participants will also be recruited via internet-based advertisements, e.g., Craigslist, Clinical Trials @ Partners, the study site's websites, RSVP for Health (which will also generate listserv emails to Partners employees, regarding research studies in need of volunteers), etc.

Participants who contact the respective study site staff in response to any of the aforementioned advertisements will complete phone screening questions to determine preliminary eligibility for the study.

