4.5 Sample Size

The NIR-flow study is expected to enroll 30 subjects, with 10 subjects who will be eligible and have analyzable data (at least 1 session post randomization).

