4.8.4 Termination

We will encourage subjects to complete the follow-up visit in the study regardless of discontinuation of the TLT sessions.

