4.17 Clinical Adverse Events

4.17.1 Overview and Definitions

All adverse events will be recorded from the time of Informed Consent through study completion, or termination. The Adverse Event CRF must be completed and submitted to the IRB, FDA, and Litecure, as required. Regulations for adverse event handling and reporting contained in the FDA and ICH Guidelines will be adhered to.

Consideration of Adverse Events will hereafter consist of Adverse Events, Serious Adverse Events, and Adverse Device Effects, including Anticipated Adverse Device Effects and Unanticipated Adverse Device Effects.

- Adverse Event is defined as any untoward/undesirable clinical occurrence in a clinical investigation of a subject using a device and/or product and which

does not necessarily have a causal relationship with this treatment. An Adverse Event can therefore be any unfavorable and/or unintended sign, symptom, or disease temporally associated with the use of a device product, whether or not considered related to the device product. Only abnormal laboratory values that are deemed clinically significant by the investigator will be classified as adverse events.

- Serious Adverse Event is defined as any untoward/undesirable adverse experience that results in any of the following outcomes: 1) death; 2) a life-threatening adverse experience; 3) inpatient hospitalization or prolongation of existing hospitalization; 4) a permanent/persistent or significant disability/incapacity or a congenital anomaly/birth defect; 5) important medical events that may not result in death, be life-threatening, or require hospitalization may be considered a serious adverse experience when, based upon appropriate medical judgment, they may jeopardize the subject and may require medical or surgical intervention to prevent one of the outcomes listed in this definition.
- Anticipated Adverse Device Effect is defined as any adverse effect related to the device or procedure, which is identified in the protocol.

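### The planned adverse event table is split only by event type, so it does not carry through the per-session safety endpoint or describe continuous and pulsed light separately, and the base of its percent is not stated

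*Combined protocol and SAP*

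**What the plan says.** Section 5.6 contains a single sentence on adverse events: "The number and percent of Adverse Events through study completion will be presented by adverse event type". Event type is the only breakdown. Section 5.7 adds general summaries: "Descriptive statistics for safety endpoints will include number of subjects", followed by the usual statistics for continuous and categorical variables. Neither section names a mode, a session, a safety population or a denominator, and no other section does so for safety.

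Three other places set what the safety analysis has to serve:

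- Section 4.1, aim 5: "To assess the safety and tolerability of the Transcranial Continuous and Pulse Near-Infrared Light Therapy in healthy subjects".
- Section 1 (Study Summary, Endpoints), where the safety endpoint is "any reported adverse events within one week from each sessions of TLT".
- Section 4.17.1, on recording: "All adverse events will be recorded from the time of Informed Consent through study completion, or termination".

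Section 4.8.2 fixes the mode by visit for every subject: continuous light at Visit 2, sham at Visit 3, pulsed light at Visit 4.

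On numbers, section 4.3.1 says "We expect to enroll 30 subjects in order to have 10 who are eligible and complete the study", while section 4.5 speaks of 30 enrolled, "with 10 subjects who will be eligible and have analyzable data (at least 1 session post randomization". Section 4.8.4 adds: "We will encourage subjects to complete the follow-up visit in the study regardless of discontinuation of the TLT sessions".

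**The concern.** The endpoint is defined session by session and the aim names two forms of light, but the only adverse event table described runs across the whole study. Followed as written, it puts four kinds of time into each row: before any session, and after each of the three modes. A reader could not see from it what followed continuous light, what followed pulsed light, or what followed a session with no light. The efficacy analysis in section 5.5 does keep the three modes apart.

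Sorting by event type does not replace the split. Section 4.20.1 lists application site discomfort among events reported with the treatment, and section 4.17.2 says the EEG headset can also cause discomfort. The headset is used before and after every session, including sham. The sham week is therefore the only in-trial reference for events that come from the procedures alone, and the planned table does not show it.

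The percent has a separate problem. Read literally it is a percent of events, and if subjects are meant, the plan does not say which subjects.

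**Working it through.** The plan gives no expected event rate and no safety sample size, so there is no figure of its own to reproduce. The check sets the sections side by side and adds simple arithmetic.

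**1. Time covered.** Screening is in Week 1, sessions are in Weeks 2, 3 and 4, and follow-up is in Week 5 (section 4.7). With visits one week apart, consent to follow-up is about 4 weeks, and the three one-week windows cover about 3 of them. The remaining week comes before any exposure: inside the section 5.6 table, outside the endpoint. Subjects who fail screening contribute only such time. Section 4.8.2 also lets the schedule shift by a week after a missed session, so some events can fall more than 7 days after a session.

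**2. What one pooled count hides (assumed range).** Suppose k subjects each have one event of a given type after some session, with k from 1 to 3. The number of ways to divide k over three modes is (k+2)(k+1)/2:

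- k = 1: 3 × 2 / 2 = 3
- k = 2: 4 × 3 / 2 = 6
- k = 3: 5 × 4 / 2 = 10

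The pulsed-light count can be anything from 0 to k. For k = 3 with 10 subjects exposed, the two extremes are:

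| Where the 3 events fell | Pulsed light | Exact 95% interval (Clopper-Pearson) | Pooled over 10 × 3 = 30 sessions |
|---|---|---|---|
| All after sham | 0/10 = 0% | 0% to 30.8% | 3/30 = 10.0% |
| All after pulsed light | 3/10 = 30.0% | 6.7% to 65.2% | 3/30 = 10.0% |

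The section 5.6 row is the same in both cases.

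**3. Base of the percent.** Sections 4.5 and 5.1 give 30 enrolled and 10 treated.

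- One affected subject among those treated: 1/10 = 10.0%.
- The same subject among those enrolled: 1/30 = 3.3%.
- One event over all sessions: 1/30 = 3.3%.
- As a share of all events, the figure depends on the total and has no fixed value.

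**4. Number exposed to each mode.** Section 4.3.1 expects 10 completers, but section 4.5 counts a subject with one session as analyzable. In the fixed order that session is continuous light. If anyone stops early, the number exposed falls from continuous light to sham to pulsed light. The documents do not say by how much. They do show that n per mode must be printed, not presumed.

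**5. Whether the split can be made.** Section 4.17.3 requires an onset date for every event. The adverse event form is completed before each session and at Week 5 (sections 4.8.2 and 4.8.3), and visit determines mode. No new data are needed.

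**6. What the split can deliver.** For 0 of 10 affected, the upper limit is 1 − 0.025^(1/10) = 30.8%. For an assumed true risk of 5% to 10% per session, the chance of seeing at least one affected subject in a mode is 1 − 0.95^10 = 0.40 to 1 − 0.90^10 = 0.65.

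**The case against.** The best reply is that a per-session summary is already implied. The Study Summary attaches the endpoint to each session, each session has one mode, and section 5.7 promises frequencies and percentages for safety endpoints. Read together, these may well mean a table by mode. That reading is fair, and it means the one-week window is already fixed in advance. It does not settle the matter: section 5.6 states a different scope for adverse events, and neither section names the mode or the base of the percent.

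A reader might infer that the trial cannot separate the safety of the modes at all. The documents do not support that. Onset date and relationship to the device or procedure are recorded for every event, skin is inspected before and after treatment, and a self-report questionnaire on discomfort follows every session, sham included. Only the planned table lacks the separation.

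A reader might also infer that substantial drop-out before pulsed light is expected. It is not: section 4.2 has all eligible subjects receiving all three sessions, section 5.5 analyses all ten, and a missed session can be made up. A falling denominator is possible, not forecast.

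Finally, aim 5 states no comparison with sham, the fixed order ties mode to period and carry-over, and the intervals are very wide. All of that stands. It rules out testing and firm attribution of an event to light or headset. It does not argue against showing each mode's counts.

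**Conclusion.** The concern holds for the planned output. As written, section 5.6 does not deliver the per-session endpoint or describe each active mode in aim 5, and its percent has no stated base. The arithmetic rests on 10 subjects per mode and an assumed one to three affected subjects. With three, an identical pooled row covers anything from 0/10 to 3/10 after pulsed light. The choice of base alone moves one affected subject from 10.0% to 3.3%.

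It would be too strong to say that every choice is left until the data are seen. The window is set; the handling of late events and the denominator are open. It would also be too strong to expect a by-mode table to show that one mode is safer than another. The change is worth making because it is cheap and serves a stated aim. It does not touch the primary blood flow analysis.

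A minor wording conflict sits alongside. Section 4.9 describes the adverse event form as capturing events related to the treatment, while sections 4.17.1 and 4.17.3 require all events. The schedule marks the form at Week 1, before any session, so section 4.9 is probably loose wording.

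**What to change.** In section 5.6:

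- Tabulate the number and percent of subjects with at least one event, plus event counts, by event type and by mode of the most recent session (continuous, sham, pulsed).
- Assign events by onset date, using the one-week window in the Study Summary.
- Take the subjects who received that session as the denominator, and print n for each mode.
- List separately, as counts without percents, events before the first session, events in screen failures, and events more than 7 days after a session.
- Present the table descriptively, without tests. State that the fixed order confounds mode with period and carry-over, and that about 10 subjects per mode gives wide limits.

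In section 5.7, refer to the same window and denominators. In section 4.9, reconcile the description of the adverse event form with sections 4.17.1 and 4.17.3.

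The cost is a few more table columns, with sparse and imprecise cells, and a few sentences of text. No additional data collection is needed.

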6.1 Ethical Review

Prior to the start of the study the Investigator will obtain IRB approval of the protocol and the Informed Consent Form. Additional documentation may be required pending applicable local requirements. At least the following documentation must be obtained:

1. The IRB/EC approval of the protocol.
2. The IRB/EC approval of the Informed Consent Form.
3. The IRB/EC annual (or any other frequency when applicable – i.e. quarterly, semiannually according to the local IRB/EC standard operating procedure) renewed approval of the protocol.
4. The IRB/EC approval of any revisions to the Informed Consent Form or amendments to the protocol.

6.2 Regulatory Considerations

This study will be conducted in accordance with the Good Clinical Practice (GCP) guidelines and other applicable regulatory requirements including but not limited to:

- The Food and Drug Administration (FDA) Regulations on Investigational Device Exemption (21 CFR 812),
- The FDA Regulations on research with human beings (21 CFR 50, 54 and 56),
- The Health and Human Services (DHHS) Regulations on research with human beings (45 CFR 46 Subparts A, B, C, and D) and
- The International Conference on Harmonization (ICH) “Guidance for Industry-E6 Good Clinical Practice: Consolidated Guideline.”

The Study will be conducted in the US in accordance with the Privacy Rule (45 CFR Parts 160 and 164) of the Health Insurance Portability and Accountability Act of 1996 (HIPAA).

6.3 Monitoring Procedures

Monitoring will be conducted by the PI who will periodically review lab results and clinical information. The PI will be coordinating the different phases of the protocol implementation such as TLT delivery and follow up. The PI will be frequently in contact with the other staff members responsible for TLT delivery and with Litecure Inc, which will lend the TLT device. We have minimized risks potentially associated with the use of Transcranial Light Therapy (TLT) by requiring two methods of contraception (although TLT has not been associated with teratogenic effect). In addition, we are providing the subjects with safety goggles or eye pads during the TLT delivery. We have also included treatment discontinuation rules based on the

development of skin erythema, pain or discomfort lasting more than 24 hours at the sites of TLT delivery (to prevent risk of subject's having an unknown skin photosensitivity).

6.3.1 Training of study site personnel

Training will be initiated prior to the protocol being implemented. Training will consist of both lecture and practicum. Application of TLT procedure will be performed only by PI or his/her designee trained by the Sponsor (or its designee) to perform the procedure.

6.4 Informed Consent

The Principal Investigator will be responsible for developing the Informed Consent Form. The Informed Consent Form will be prepared in accordance with FDA 21 CFR Part 50 for all US sites. The Informed Consent Form will be used to explain in simple terms, before the subject is entered into the study, the possible risks and benefits to the subject. The Informed Consent Form will contain a statement that the consent is freely given, that the subject is aware of the risks and benefits of entering the study, and that the subject is free to withdraw from the study at any time.

Prior to a subject's participation in the study, the written Informed Consent Form will be signed and personally dated by the subject or by an individual authorized to sign on behalf of the subject per compliance with local regulations.

If a subject is unable to read or if a legal representative is unable to read, an impartial witness will be present during the entire Informed Consent Form discussion. After the written Informed Consent Form and any other written information to be provided to the subject is read and explained to the subject or legal representative, and oral consent to the subject's participation in the study has been given by the subject, the witness will sign and date the Consent Form.

A witness in the consent process is considered to be an individual that is impartial and independent of the study.

Note: *The Investigator must document acquisition of the written Informed Consent Form in the subject's medical records, and the subject or legal representative must be given a copy of the Informed Consent Form document prior to enrollment into the study.*

6.5 Protocol Adherence

The protocol must be read and followed by all participating study personnel.

